9.4.2 Analysis of the Primary Efficacy Endpoint(s)

[Aim 1: To assess clinical efficacy of HDS-TBS.

Hypothesis 1: Compared with sham, active TMS will result in a greater reduction in depressive symptoms by the end of the treatment period. Each patient will receive either one five day sham or one 5-day active treatment.

The primary outcome will be based on the set of repeated Montgomery Asberg Depression scores obtained at baseline and on each of the five treatment days. We will use linear mixed effects models to compare the two treatment groups on change from baseline across the five days. As noted above, the response may be transformed to reduce levels of skewness. The main fixed effects will be the treatment group indicator, and we expect that a random intercept will accommodate the within person correlations over the five daily measures of change.

Power for Hypothesis 1: We use the methods of Hedeker, Gibbons and Waternaux [13]. For a random intercept model with correlation coefficient of rho=0.3, we have 80% power for a group effect of Cohen's d=0.72.

Estimated regression coefficients will be reported, along with standard errors, associated confidence intervals, and p-values for hypothesis tests. In analyses adjusting for covariates, adjusted least squares means for treatment groups will be reported.

Little missing data is expected for the baseline and five-day treatment period. The mixed effects models used for Hypothesis 1 will use any data, partial or complete, provided by the randomized participants, and will yield valid estimates under missing-at-random assumptions.]

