3 STUDY OBJECTIVES AND ENDPOINTS

OBJECTIVES	ENDPOINTS	JUSTIFICATION FOR ENDPOINTS
Primary		
The primary objective is to assess clinical efficacy of HDS-TBS.	The primary outcome will be response to TMS treatment as evidenced by change in the Montgomery Asberg Depression from the pre-treatment baseline to the end of the 5-day treatment course.	We have used the MADRS in many prior studies. The MADRS will be the primary outcome measure of current depression severity as this scale was designed to be sensitive to change.
Secondary		
The secondary objective(s) are to determine the effect of iTBS on DLPFC rfMRI and establish a relationship between change in brain resting state functional connectivity and treatment effects.	To assess the effect of active HDS-TBS on the functional connectome, we will test for differences in DLPFC-SGACC connectivity between the active- treated and sham-treated after 5 days of treatment.	We will examine the connectivity between DLPFC-SGACC, using the DLPFC stimulation site, identified on neuronavigation and an a priori defined SGACC ROI.
Tertiary		
N/A	N/A	N/A

[MagPro X100 Stimulator, Cool-B65 Butterfly Coil]

Page 16 of 39

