5 STUDY POPULATION

5.1 Inclusion Criteria

[In order to be eligible to participate in this study, an individual must meet all of the following criteria:

- Bipolar depression (BP I and BP II) by DSM 5 criteria [8]
- Age 18-70
- Right or left handed
- All genders
- Treatment resistant depression, as in they must have treatment resistant depression with 2 or more prior antidepressant trials that have failed to produce a response (> 50% reduction in symptoms) using ATHF criteria [9]
- Able to provide informed consent to participate in the study
- Must be on a stable medication regimen, requiring at least one mood stabilizer
- Depression severity as represented by scoring at least 20 on MADRS

If unsure about participants' eligibility, the research team may contact the participants' treatment provider (i.e. psychologist, nurse practitioner, psychiatrist) to gather additional information to make a determination.]

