8 STUDY ASSESSMENT AND PROCEDURES

8.1 Efficacy Assessments

[Participants complete the following for screening: Structured interview for Diagnostic and Statistical Manual of Mental Disorders 5th Edition (DSM-V), the Montgomery-Asberg Depression Rating Scale (MADRS), the Young Mania Rating Scale (YMRS), the Oldfield Assessment for Handedness (handedness will be included in data analysis but is not an exclusionary criterion), and screening for dementia (MMSE >24).

Once enrolled, patients will also complete an MRI scan. MRI data will be acquired on a 3 Tesla Siemens Prisma scanner using a 64 channel head coil (Erlangen, Germany). Our acquisitions are optimized for Siemens Prisma scanners and are rigorously tested as part of the human connectome project (HCP). In the rs-fMRI targeting session T1-weighted, T2-weighted, , and rs-fMRI (2x 8 min) scans will be collected using the 64-channel head coil. We will use the structural and diffusion data to create finite-element models of the electric field for varying coil orientations at the individualized site of stimulation and use these models to optimize the coil orientation for each subject [12].

Patients will complete the TMS administration for 5 consecutive days. They will also complete the MADRS on each day. Following completion of treatment, participants will complete another MRI scan and another MADRS. Patients will also complete a Scale for Suicide Ideation (SSI) and neurocognitive assessments pre and post-treatment.

The data collected to be included in efficacy analyses (pre- and post-treatment) will be the measures of depression severity (MADRS), Antidepressant Treatment History Form (ATHF) data, psychotropic medication at baseline, an optional "The Battleship Task" computational task (which examines how well participants are able to learn a set of shapes that are hidden in a grid), and resting state functional connectivity data (using DLPFC as a seed regions). The primary outcomes will be response to TMS as evidenced by change in MADRS scores for depression severity from the pre-treatment baseline to the end of the 5-day treatment course. The secondary outcome will be change in functional connectivity from pre-treatment to post-treatment using MRI of the brain.]

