12 APPENDIX

12.1 Schedule of Activities (SoA)

Procedures	Screening	Enrollment/ Baseline	TMS Session Day 1	TMS Session Day 2	TMS Session Day 3	TMS Session Day 4	TMS Session Day 5	Post Stimulation	Follow- Up Visit (4 weeks)
Informed consent	X								
Demographics	X								
Medical history	X								
SCID	X								
MADRS	X		X	X	X	X	X	X	X
HAM-D	X							X	X
SSI	X		X	X	X	X	X	X	X
YMRS	X		X	X	X	X	X	X	X
Oldfield Assessment for Handedness	X								
MMSE	X								
The Battleship Task		X						X	
Randomization		X							
MRI		X		X*	X*			X	
Motor Threshold		X							
Neurocognitive assessments		X						X	
TMS treatment (1 session every 50 minutes, 10			X	X	X	X	X		

[MagPro X100 Stimulator, Cool-B65 Butterfly Coil]

Page 39 of 39

sessions per day)								
Self Report Questionnaires	X	X	X	X	X	X	X	X

^{*}MRI: Optional MRI scan on Day 2 or 3 of TMS treatment.

END OF DOCUMENT

^{**}Battleship Task: Optional task given at baseline and post treatment

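### Read literally, the primary MADRS set counts Day 1 as an outcome, leaves out the Post Stimulation rating and averages over days, so it understates an end-of-course effect that builds during treatment.

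*Combined protocol and SAP*

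**What the plan says.** Section 3 defines the primary outcome as "change in the Montgomery Asberg Depression from the pre-treatment baseline to the end of the 5-day treatment course". Section 8.1 says the same in substance, and Hypothesis 1 is also framed at the end of treatment.

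Sections 9.1 and 9.4.2 define the data differently: the outcome rests on the "set of repeated Montgomery Asberg Depression scores obtained at baseline and on each of the five treatment days". Section 9.4.2 adds that "The main fixed effects will be the treatment group indicator" and expects that "a random intercept will accommodate the within person correlations over the five daily measures of change". It names no day effect and no group-by-day term. Baseline MADRS is not among the covariates in section 9.4.1.

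In the Schedule of Activities (12.1) the MADRS row has eight marks for nine visit columns: Screening, TMS Days 1 to 5, Post Stimulation and the 4-week visit. The empty cell is Enrollment/Baseline.

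The screening MADRS also applies an entry criterion (5.1): "Depression severity as represented by scoring at least 20 on MADRS". Section 8.1 confirms a rating after the course: "Following completion of treatment, participants will complete another MRI scan and another MADRS". Sections 8.1 and 9.4.1 both describe the efficacy data, MADRS included, as taken before and after treatment.

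No section names the visit that supplies the analysis baseline, sets a maximum interval from screening to Day 1, or says whether a daily MADRS is done before or after that day's ten sessions.

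**The concern.** Five daily measures of change need five post-baseline ratings plus a separate baseline. With MADRS on Days 1 to 5 and none at Enrollment/Baseline, Day 1 must be one of the five outcomes, and screening is the only scheduled rating left to start from. The Post Stimulation MADRS, the only rating before follow-up that is certain to come after the full course, is then not used.

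The question in section 3 concerns the end of the course. A single group indicator over five daily changes estimates the average difference across the course. That average includes the day with least exposure, which has no exposure at all if raters see participants before the first session. If the effect accumulates, the estimate is smaller than the quantity the trial sets out to measure. With 32 usable participants there is little room for that loss.

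**Working it through.** **Inputs from the documents.** 34 participants with 32 usable (1.1); rho = 0.3, d = 0.72 and 80% power (9.2); five daily measures of change (9.4.2). **Assumed because not stated:** 1:1 allocation (16 per arm) and two-sided alpha 0.05.

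**1. The plan's own figure.** The mean of m equally correlated measures has variance factor v = (1 + (m − 1)rho)/m. The standard error of the arm difference in SD units is sqrt(2v/16), and power = Φ(effect/SE − 1.96).
- m = 5: v = (1 + 4 × 0.3)/5 = 0.44; SE = 0.2345; power for 0.72 = Φ(3.07 − 1.96) = 86.7% (84.4% by noncentral t).
- m = 3: v = 0.533; SE = 0.258; power = 79.6%.

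The stated 80% is therefore not reproduced with five measures; it matches three. For its own inputs it is conservative. It treats d = 0.72 as the effect averaged over the outcome days.

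**2. Share of the end-of-course effect captured.** Assume linear build-up over five days, then a plateau.
- Ratings after the day's sessions: Days 1-5 carry 0.2, 0.4, 0.6, 0.8, 1.0 and Post carries 1.0. Mean of Days 1-5 = 3.0/5 = 60%. Mean of Days 2-5 plus Post = 3.8/5 = 76%.
- Ratings before the sessions: Days 1-5 carry 0, 0.2, 0.4, 0.6, 0.8 and Post carries 1.0. Mean of Days 1-5 = 2.0/5 = 40%. Mean of Days 2-5 plus Post = 3.0/5 = 60%.
- Post Stimulation alone: 100% either way.

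**3. Power.** Assume an end-of-course effect of 1.0 SD of change, with that SD held fixed. SE is 0.2345 for a mean of five and sqrt(2/16) = 0.3536 for one rating.

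| Outcome | Ratings after sessions | Ratings before sessions |
|---|---|---|
| Days 1-5 averaged | Φ(0.60/0.2345 − 1.96) = 72.5% | Φ(0.40/0.2345 − 1.96) = 40.0% |
| Days 2-5 plus Post averaged | Φ(0.76/0.2345 − 1.96) = 90.0% | 72.5% |
| Post alone | Φ(1/0.3536 − 1.96) = 80.7% | 80.7% |

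If the plan's 0.72 were the end-of-course effect, the Day 1-5 average would be 0.72 × 0.60 = 0.43 SD (power 45.3%) or 0.72 × 0.40 = 0.29 SD (23.2%).

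**4. Sensitivity to rho.** Changes that share one baseline correlate 0.5 when raw scores are exchangeable with equal variances. Then v = 0.6 and SE = 0.2739. The first row becomes 59.1% or 30.9%, the second 79.2% or 59.1%, and Post alone stays at 80.7%.

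**5. Screening as baseline.** Participation of 6-8 weeks, less 28 days of follow-up and a 5-10 day course, leaves 42 − 28 − 10 = 4 to 56 − 28 − 5 = 23 days for everything else, so the screening score need not be recent. Let daily ratings correlate 0.8 with each other and screening correlate r with them, at equal variances. The variance of mean change is 0.84 + 1 − 2r. Against a baseline that also correlates 0.8, the SD ratio is 1.00 at r = 0.8, 1.35 at r = 0.7 and 1.63 at r = 0.6. The documents give no value for r.

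**The case against.** **Screening is never named as the baseline.** This stands. It follows by elimination from the schedule, and the plan could equally be read as leaving the baseline undefined.

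**The Post Stimulation rating is not plainly excluded.** This also stands. A reader might infer from section 9.4.2 that it has been ruled out, but sections 8.1 and 9.4.1 describe the efficacy data as taken before and after treatment. Those statements conflict with the set in 9.1 and 9.4.2, and the documents do not settle which governs.

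**Much of the shortfall comes from averaging, not from Day 1.** Correct. Swapping Day 1 for Post Stimulation raises the captured share only to 76% or 60%. A contrast at the end-of-treatment rating is needed to reach 100%.

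**The trajectory is assumed.** Also correct. If the full effect were present by the Day 1 rating and held, nothing would be diluted and averaging would be the stronger analysis: Φ(1/0.2345 − 1.96) = 98.9% against 80.7%. And if ratings follow the sessions, Day 5 already reflects the full course and would meet the endpoint in section 3. The plan gives no reason to expect an immediate full effect, and it states its hypothesis at the end of treatment.

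**Two stronger readings fail.** One is that the entry threshold biases the result. Regression to the mean from that threshold is expected equally in both randomized arms, so it does not bias the between-arm contrast. The other is that a screening baseline certainly adds noise. It does so only if it correlates less with treatment-day ratings than a Day 1 pre-session rating would; with equal correlations the ratio is 1.00.

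**Conclusion.** The point holds as a mismatch between the stated endpoint and the data and contrast that section 9.4.2 specifies. It goes beyond missing detail: following that section as written averages in the least-exposed day and omits the one pre-follow-up rating certain to follow full treatment.

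The loss is conditional on an effect that accumulates over the course. The 60% and 40% shares rest on linear build-up. The power figures also rest on a 1.0 SD end-of-course effect, 16 per arm, rho 0.3, two-sided 0.05 and a fixed SD of change. They illustrate the size and do not predict this trial's power. A reader might conclude that the trial is underpowered, but the documents do not say whether d = 0.72 is an average or an end-of-course effect, so that does not follow. Extra noise from a screening baseline is possible but not quantified by anything in the plan.

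**What to change.** 1. Rate the already-scheduled Day 1 MADRS before the first session and name it the analysis baseline. Keep the screening MADRS for eligibility only.
2. Use Days 2-5 and the already-scheduled Post Stimulation MADRS as the post-baseline outcomes.
3. Include day and group-by-day terms, with the primary contrast at Post Stimulation as the end-of-treatment rating. Report the average over days as supportive.
4. Adjust for baseline MADRS.
5. State when the Day 2-5 ratings are done relative to that day's sessions, identically in both arms.
6. Reconcile sections 3, 8.1 and 9.4.1 with 9.1 and 9.4.2.

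No assessment is added; the cost is SAP wording and a timing instruction to raters. The statistical price is that a single-time-point contrast gives up some precision from averaging: on the assumptions above, 80.7% against 90.0% for Days 2-5 plus Post with after-session ratings at rho 0.3, although that advantage is gone at rho 0.5 (79.2%). Section 9.2 should therefore restate power for the chosen contrast, with alpha, sidedness, allocation and number of measures given.

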4 STUDY PLAN

4.1 Study Design

[Hypothesis 1: The null hypothesis is that there will be no difference in reductions in depressive symptoms by the end of the five-day treatment period. The alternative hypothesis is that, compared with sham, active TMS will result in a greater reduction in depressive symptoms by the end of the treatment period.

Hypothesis 2: The null hypothesis is that there will be no difference in the change in correlation from pretreatment to post-treatment between the active and sham groups. The alternative hypothesis is that, compared with sham, active TMS will result in a greater increase in correlation of the dorsal lateral prefrontal cortex (DLPFC) with limbic regions, in particular with the subgenual cingulate cortex (SGACC). This is a superiority comparison, for active relative to sham.

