9 STATISTICAL CONSIDERATIONS

9.1 Statistical Hypotheses

Primary Efficacy Endpoint(s):

[MagPro X100 Stimulator, Cool-B65 Butterfly Coil]

Page 29 of 39

[The primary outcome will be based on the set of repeated Montgomery Asberg Depression scores obtained at baseline and on each of the five treatment days.

Hypothesis 1: The null hypothesis is that there will be no difference in reductions in depressive symptoms by the end of the five-day treatment period. The alternative hypothesis is that, compared with sham, active TMS will result in a greater reduction in depressive symptoms by the end of the treatment period. This is a superiority comparison, for active relative to sham.]

• Secondary Efficacy Endpoint(s):

[The main secondary outcome will be the change in correlation of the dorsal lateral prefrontal cortex (DLPFC) with limbic regions, in particular with the subgenual cingulate cortex (SGACC).

Hypothesis 2: The null hypothesis is that there will be no difference in the change in correlation from pre-treatment to post-treatment between the active and sham groups. The alternative hypothesis is that, compared with sham, active TMS will result in a greater increase in correlation of the dorsal lateral prefrontal cortex (DLPFC) with limbic regions, in particular with the subgenual cingulate cortex (SGACC). This is a superiority comparison, for active relative to sham.]

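### The primary endpoint is MADRS change to the end of the 5-day course, but the primary model tests a Day 1-5 average and names no end-of-treatment contrast

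*Combined protocol and SAP*

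**What the plan says.** Three places fix the endpoint at the end of treatment:

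- Section 3 takes MADRS change "from the pre-treatment baseline to the end of the 5-day treatment course".
- Section 8.1 repeats it as "change in MADRS scores for depression severity from the pre-treatment baseline to the end of the 5-day treatment course".
- Hypothesis 1 follows suit. The null in section 4.1 is that "there will be no difference in reductions in depressive symptoms by the end of the five-day treatment period", and the alternative in section 9.1 is that "active TMS will result in a greater reduction in depressive symptoms by the end of the treatment period". Section 9.4.2 restates the alternative.

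The statistical sections then move to the whole course. Sections 9.1 and 9.4.2 base the outcome on "the set of repeated Montgomery Asberg Depression scores obtained at baseline and on each of the five treatment days". The comparison in 9.4.2 is: "We will use linear mixed effects models to compare the two treatment groups on change from baseline across the five days". The only fixed effect it names is the treatment group indicator. For the correlation among a participant's repeated ratings, the authors write: "we expect that a random intercept will accommodate the within person correlations over the five daily measures of change".

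Section 9.4.1 adds baseline covariates and leaves the daily trajectory to descriptive statistics and plots. Section 9.2 frames power as a group effect over the five days: 80% at Cohen's d = 0.72, using a random intercept model with rho = 0.3. No section names a treatment-by-day term or a contrast at Day 5 or at the Post Stimulation visit.

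**The concern.** The endpoint is a difference at one time point, while the model as described delivers a difference averaged over five. Day 5 is in the model, but it is pooled with Days 1-4 and never tested alone.

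This is the trial's only primary hypothesis; section 9.2 treats everything further as exploratory. The headline estimate, confidence interval and p-value would therefore describe a quantity that the endpoint section does not define. If benefit builds over the week, the reported effect understates the end-of-treatment effect, and the interval misses it more often than its nominal 5%. No power is stated for the endpoint that sections 3 and 8.1 declare.

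**Working it through.** **Inputs.** From the documents: rho = 0.3, d = 0.72 and 80% power (9.2, 9.4.2); five daily changes (9.4.2); 34 participants with 32 usable (1.1). Assumed because not stated: 1:1 allocation (16 per arm), two-sided alpha 0.05, rho read as the correlation between daily change scores, and d in SD units of one change score.

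**1. What the coefficient estimates.** With complete data, a treatment indicator and a random intercept, the coefficient is the between-group difference in each person's mean of five changes. A day main effect is balanced across arms and does not alter it. In 60 fitted models the coefficient equalled that difference to within 1e-15, with or without a day effect.

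**2. The plan's own power figure.** The variance of a five-day mean is (1 + 4 × 0.3)/5 = 0.44. The standard error of the group difference is √(2 × 0.44/16) = 0.2345, and the noncentrality is 0.72/0.2345 = 3.07. With 30 df, power is 84.4%, and 80% is reached at d = 0.68. The stated 80% at 0.72 is thus not exactly reproduced; it would need rho = 0.37, or 14-15 per arm at rho = 0.3 (78.9% and 81.8%).

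**3. Power of a single end-of-treatment contrast.** The standard error is √(2/16) = 0.3536, the noncentrality 0.72/0.3536 = 2.04, and power 50.4%. Reaching 80% needs d of about 1.02, or 32 per arm (80.9%).

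**4. Average against end effect.** Let k be the average effect divided by the Day 5 effect, with the Day 5 effect set at 0.72. The documents give no day-by-day effects, so the four courses are illustrations. The effects on Days 1 to 5, as fractions of the Day 5 effect, are:

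- constant: 1 throughout, k = 1.00
- Day 3 plateau: 1/3, 2/3, 1, 1, 1, k = 4/5 = 0.80
- square root: √(i/5) on day i, k = 0.75
- linear: 0.2, 0.4, 0.6, 0.8, 1.0, k = 3/5 = 0.60

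The coefficient targets 0.72k. Power uses noncentrality 0.72k/0.2345. Coverage of the end effect is the probability that a noncentral t (30 df, noncentrality 0.72(1 − k)/0.2345) lies within ±2.042.

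| Course | Coefficient targets | Power of averaged test | 95% CI coverage of end effect |
|---|---|---|---|
| Constant | 0.72 | 84% | 95% |
| Day 3 plateau | 0.58 | 66% | 91% |
| Square root | 0.54 | 61% | 88% |
| Linear | 0.43 | 43% | 78% |

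A simulation of 20,000 trials agreed: mean estimates 0.720 / 0.575 / 0.539 / 0.435, power 84.2 / 66.2 / 60.2 / 43.6%, coverage 94.9 / 90.6 / 88.4 / 77.9%. The Day 5 contrast kept about 50% power and 95% coverage in all four courses.

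**5. Break-even.** Averaging gains power over the single contrast only when k exceeds √0.44 = 0.66.

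**6. Sensitivity to rho.** If the random intercept applies to raw scores, subtracting baseline leaves changes with variance 2σ² and covariance σ², a correlation of 0.5. The variance factor becomes (1 + 4 × 0.5)/5 = 0.60. Power is then 72 / 53 / 48 / 33% and coverage 95 / 92 / 90 / 82%.

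**The case against.** There are four serious points on the other side.

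- **The specification is incomplete, not wrong.** Section 9.4.2 speaks of main fixed effects, which need not mean the only ones, and nothing forbids a time or interaction term. That is true. But a contrast that is not named is not prespecified, and the comparison that is named runs over all five days.
- **Section 9 is largely consistent with an average.** Outcome, comparison and sample size all refer to repeated scores or to the five days, so the team may simply mean the average. If so, sections 3 and 8.1 and Hypothesis 1 need rewriting; the conflict remains until they are.
- **The power argument depends on an unstated alpha.** A single contrast adjusted for baseline MADRS, with baseline-to-end correlation 0.3 and one-sided 0.05, has 79.4% power with 16 per arm, close to the stated 80%. However, baseline MADRS is not among the covariates in 9.4.1, and 9.2 attaches its figure to a random intercept model over five days. Without that adjustment, one-sided 0.05 gives 64%.
- **The harm depends on assumed time courses, and averaging can be better.** Both parts stand. With a constant effect there is no bias, and the average has 84% power against 50%. The daily plots in 9.4.1 would also show a Day 5 difference, though without a test. The mismatch between endpoint and test does not depend on any time course.

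**Conclusion.** The concern holds and must be fixed. Sections 3 and 8.1 and Hypothesis 1 state one target, and 9.4.2 tests another. The mismatch follows from the text and the algebra of the model; its size depends on how the effect develops. Across the illustrated courses the coefficient is 60-100% of the end-of-treatment effect, and CI coverage of that effect is 78-95% (82-95% if change scores correlate 0.5). The stated 80% power belongs to a repeated-measures average; an unadjusted single end-of-treatment contrast has about 50%. These figures assume 16 per arm, two-sided 0.05 and complete data. The test of no treatment effect keeps its type I error.

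**What to change.** Choose one target and make every section match it.

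**If the endpoint is the end of treatment.** In 9.4.2, model post-baseline MADRS with categorical day, treatment, treatment-by-day and baseline MADRS. Make the treatment contrast at one named rating the primary test. The schedule in 12.1 has a MADRS on Day 5 and another at Post Stimulation, so state which is the end; if it is Post Stimulation, add that visit to the model. Report the across-days average as secondary. Align sections 3, 8.1, 9.1 and 9.2, and restate power for the named contrast with alpha and sidedness.

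**If the endpoint is the five-day average.** Rewrite sections 3 and 8.1 and Hypothesis 1 to say so, and keep the model.

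**Cost.** No new data are needed, because the ratings are already scheduled. The first option carries a less favourable power statement. Adjusting for baseline multiplies the change-score variance by (1 + r)/2, where r is the assumed correlation of baseline with end raw scores (equal variances, 29 df):

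| Single contrast | Power at d = 0.72, 16 per arm | d for 80% | Total N for 80% at d = 0.72 |
|---|---|---|---|
| Unadjusted | 50% | 1.02 | 64 |
| Adjusted, r = 0.3 | 69% | 0.83 | 42 |
| Adjusted, r = 0.5 | 62% | 0.89 | 48 |
| Adjusted, r = 0.7 | 57% | 0.94 | 54 |

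If the team expects an early and sustained effect, the 84% power of the average is a sound reason to choose the second option openly.
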